1. PURPOSE

The objective of this study is to assess INVSENSOR00011's clinical performance for detection of a subject's position and posture in bed, subject's activity (sitting, standing, etc.) [REDACTED] and respiratory rate. Only noninvasive sensors and corresponding devices will be employed to collect data from healthy volunteers in this study.

This is a nonrandomized single arm study where all of the subjects are enrolled into the experimental arm and will receive the INVSENSOR00011 device on their chest or back, along with a RAM (Rainbow Acoustic Monitoring) sensor on their neck, a pulse oximeter on their finger, and a nasal cannula which will be attached to the capnography device.

Outcome Measure: Assess the clinical performance of the detection of position, posture and activity through comparing INVSENSOR00011 measurements to observer's notes. Assess INVSENSOR00011's [REDACTED] respiratory rate measurements through comparison with those from [REDACTED] RAM.

2. BACKGROUND

Masimo Corporation develops non-invasive medical technologies. These devices have applications in the operating room, critical care unit, emergency room, emergency transport vehicles, as well as physician's offices.

2.1. Background and Rationale

People with the most risk of developing bedsores are those with a medical condition that limits their ability to change positions, requires them to use a wheelchair or confines them to a bed for a long time.

Bedsores can develop quickly and are often difficult to treat. Automated detection of patients' position can help medical staff monitor position to time and optimize interventions. Masimo has developed a new noninvasive sensor named INVSENSOR00011 as a device to aid in preventing hospital-acquired pressure injury or worsening of existing pressure injury by monitoring patient movement, position, and orientation. The sensor is also able to detect falls through the same monitoring features. This type of monitoring may be effective in reducing the debilitating conditions for patients and their duration of stay in hospitals, especially in the patient population vulnerable to pressure and/or fall related injuries.

Each year over 2.5 million individuals in the U.S. develop a pressure injury [1]. Pressure injuries are painful, debilitating and are usually avoidable. Routine repositioning relieves and redistributes pressure over bony prominences; it is a recommended procedure to help mitigate the risks for developing a pressure injury [2]. The INVSENSOR00011 device, through detection of patient position, is a modality to ensure repositioning occurs routinely.

As many as 1 million Americans fall in the hospital every year. Falls result in fractures, lacerations, bleeding and even death. Current practices to prevent falls include assessment of patient risk, scheduled rounding practices and patient specific interventions to prevent falls [3]. The INVSENSOR00011 device is proposed to supplement current practices with a unique modality to assess risk for fall based on patient position.

The INVSENSOR00011 system consists of a wearable, battery-operated, adhesive sensor and a back-end user interface and display at the patient bedside as well as a central location (e.g., nursing station). The sensor contains sensing elements (accelerometers, gyroscopes), processor, and a blue-tooth communication chip (BTLE 2.4 GHz). An algorithm processes three-dimensional acceleration and rotation information and calculates the patient's relative position and fall [REDACTED] and respiration rate as its key parameters. Position related parameters are then combined over a given time period to compute trend and potential risk for pressure injury. The system can generate alarms configured for adverse events related to patient posture, stress level for pressure injury and detected fall events.

Literature Review:

1. Berlowitz, et al. (2014). Preventing pressure ulcers in hospitals: A toolkit for improving quality of care. Retrieved <http://www.ahrq.gov/sites/default/files/publications/files/putoolkit.pdf>
2. National Pressure Ulcer Advisory Panel, European Pressure Ulcer Advisory Panel and Pan Pacific Pressure Ulcer Injury Alliance. Prevention and treatment of pressure ulcers: Quick reference guide. Emily Haesler (Ed.). Cambridge Media: Perth, Australia; 2014

2.2. Study Devices

2.2.1. Investigational Devices and Sensors:

2.2.1.1. INVSENSOR00011 sensor is an investigational, non-invasive sensor that measures signals regarding patient's movement and posture [REDACTED] and respiratory rate. This sensor has undergone a risk assessment prior to use in human subjects to safeguard their safety and well-being. [REDACTED]

2.2.1.2. Root® is a noninvasive monitoring platform. [REDACTED]

[REDACTED]

[REDACTED]

2.2.2. FDA cleared Sensors and Devices:

- Masimo FDA-cleared Radical-7
- Masimo FDA-cleared RAM cloth sensor
- Masimo FDA-cleared pulse oximeter sensor
- Masimo FDA-cleared RAM dual cable

3. **REFERENCE**

3.1.1.	██████████ Rev. A	Consent 18 years and greater
3.1.2.	██████████ Rev. A	Recruitment Script
3.1.3.	██████████ Rev. A	Web Ad
3.1.4.	██████████ Rev. A	Health Questionnaire
3.1.5.	██████████ Rev. A	Gender and Ethnicity Questionnaire
3.1.6.	██████████ Rev. A	Confidentiality Agreement
3.1.7.	██████████ Rev. A	Case Report Form
3.1.8.	██████████	Device Accountability Log
3.1.9.	██████████	Protocol Deviation Report
3.1.10.	██████████	Adverse Event Form
3.1.11.	██████████	Clinical Study Request Form

4. **LOCATION**

Masimo Corporation
Clinical Laboratory
[name]
[name]

The Masimo Clinical Laboratory facility is designed as a Phase 1 clinical study research center. All personnel undergo routine required training on GCP and human subject research protections. The laboratory is equipped with standard FDA-approved medical monitoring equipment. Hospitals and urgent care facilities are within three miles of Masimo Clinical Laboratory.

5. **STUDY POPULATION**5.1. Inclusion Criteria

- 18 to 80 years old
- Physical status of ASA I or II
- Subjects must be able to read and communicate in English
- Has signed all necessary related documents, e.g. written informed consent, health assessment questionnaire, gender and ethnicity form, confidentiality agreement
- Passed Health Assessment Screening

5.2. Exclusion Criteria

- Subject has any medical condition which in the judgment of the investigator, renders them inappropriate for participation in this study
- Inability to tolerate sitting still or minimal movement for at least 30 minutes
- Nursing female volunteers
- Excluded at the Principal Investigator's discretion
- Refusal to take the pregnancy test (for female subjects)
- Positive pregnancy test for female subjects of child bearing potential. This is done for the safety of this population.
- Refusal to shave hair (neck, chest) off areas where sensors will be applied (male subjects)

5.3. Withdrawal of Subjects

Subjects must be withdrawn under the following circumstances:

- The subject withdraws consent
- Non-verbal consent withdrawal
- Serious adverse event
- Discretion of investigator
- Malfunction of the device for greater than 10 minutes

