6. EQUIPMENT AND MATERIALS

Equipment and Materials: All lab equipment will be maintained per manufacturer specifications and all study personnel will be trained on the use of relevant equipment.

Test Devices:

- INVSENSOR00011
- Root [REDACTED]

Control Devices:

- Masimo Radical-7
- Masimo pulse oximeter sensor
- Masimo RAM sensor

Research Equipment:

- Data Collection Laptop, software and other equipment as necessary to record the data

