7.5. Study Procedure

- 7.5.1. Apply sensors. [REDACTED]

- 7.5.2. [REDACTED]

- 7.5.3. [REDACTED]

[REDACTED]	[REDACTED]	[REDACTED]

[REDACTED]	[REDACTED]	[REDACTED]
[REDACTED]	[REDACTED]	[REDACTED]
[REDACTED]	[REDACTED]	[REDACTED]

7.5.4. [REDACTED] All enrolled subjects will be paid [REDACTED] after the completion of the study with no additional compensation for travel. Subjects who do not complete the study will be paid [REDACTED] with no additional compensation for travel.

7.5.5. In case of an error in following the instruction set, subject can repeat the missed steps.

7.5.6. Subjects may stop the study at any time.

7.5.7. Data collected in this study may be used in the future for product development, publications, and/or submissions to the FDA or other regulatory agencies.

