7.6. Discontinuation

[figure not shown]
7.6.1. In the event that a study is discontinued prior to completion, whether it is due to the investigator's discretion or the subject's request, the subject will be paid for their time according to the Financial Compensation chart, refer to Section 7.5.4.

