8. ACCEPTANCE CRITERIA (IF APPLICABLE)

There are no acceptance criteria. [REDACTED]

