9.3. Statistical Analysis

- 9.3.1. For each subject's position detection, INVSENSOR00011 output will be compared against observer's notes at each turn of the subject.
- 9.3.2. Correctly detected position changes will be marked as True Positive.
- 9.3.3. Missed detections (if any) will be counted.
- 9.3.4. Combining the two, sensitivity of INVSENSOR00011's posture change detection will be computed as Sensitivity = True Positive/(True Positive + Missed Detection)
- 9.3.5. From the INVSENSOR00011's output, all false positives will be counted, i.e., when a turn is indicated by INVSENSOR00011 but the observer's notes do not agree with that. These will present a measure of specificity of the device.
- 9.3.6. Heart rate readings from INVSENSOR00011 will be compared against reference pulse-rates to compute mean and standard deviation of the differences.
- 9.3.7. Respiration rate readings from INVSENSOR00011 will be compared against reference respiration rate to compute mean and standard deviation of the differences.

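### Does withdrawing subjects for malfunction of an unnamed device, with no count of the turns lost, undermine the sensitivity result?

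*Combined protocol and SAP*

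**What the plan says.** Section 5.3 lists circumstances in which a subject must be withdrawn. The last is "Malfunction of the device for greater than 10 minutes". The device is not named there. Section 6 lists two test devices (INVSENSOR00011 and Root), three control devices including the "Masimo Radical-7", and data collection equipment. Section 1 also mentions "a nasal cannula which will be attached to the capnography device".

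Section 9.3.1 sets the unit of analysis: "INVSENSOR00011 output will be compared against observer's notes at each turn of the subject". Section 9.3.2 marks correct detections as true positives and 9.3.3 counts the missed ones. Under 9.3.4 the "sensitivity of INVSENSOR00011's posture change detection will be computed as Sensitivity = True Positive/(True Positive + Missed Detection"), that is, detected turns over detected plus missed turns. The readable text of 9.3 has no line for withdrawn subjects or for turns that were not carried out.

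Section 9.1 plans 30 subjects with five or more position changes each, hence at least 150 data points, to be used for validation. Section 9.4 expects a dropout rate of about 0%. Section 8 states: "There are no acceptance criteria". Section 10 counts malfunctions among device deficiencies, puts them on the Case Report Form and has them reported under department procedures. Section 12.2 also puts device use on that form.

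**The concern.** In a device study, losing a subject because the product failed is not the same as losing one for an unrelated reason. If the sensor fails, the subject leaves and the remaining turns drop out of the calculation, so the sensitivity describes the sensor only while it works. A study with no failures and one with several could print the same percentage.

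The unnamed device adds to the doubt. Position is scored against the observer's notes, so a fault in the acoustic sensor or the pulse oximeter would leave the position reference intact, while a fault in INVSENSOR00011 concerns the product itself. Section 7.6.1, on payment after early discontinuation, does not help: it covers the case "In the event that a study is discontinued prior to completion, whether it is due to the investigator's discretion or the subject's request" and does not mention malfunction.

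What would be at stake is how the figure reads outside the study, because section 7.5.7 says: "Data collected in this study may be used in the future for product development, publications, and/or submissions to the FDA or other regulatory agencies".

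**Working it through.** **Inputs.** From section 9.1: N = 30, at least five turns per subject, turns treated as independent. From section 9.4: dropout about 0%. The documents give no malfunction rate, so the number withdrawn, k = 0, 1, 2 or 3, is an assumption, with no replacement of subjects.

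**1. The plan's own figure.** 30 × 5 = 150, which agrees with section 9.1.

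**2. Where each kind of turn goes under section 9.3.**

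| Turn | Treatment |
|---|---|
| Performed and detected | true positive (9.3.2) |
| Performed and not detected | missed detection (9.3.3) |
| Not performed after withdrawal | no observer's note, outside the formula |

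The third row is correct. Sensitivity is a proportion of events that happened, and there is no event to detect.

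**3. Heaviest loss per subject.** Each withdrawn subject leaves before any scored turn, and every performed turn is detected. Turns performed: n = 150 − 5k. Exact (Clopper-Pearson) 95% lower limit when all n are detected: 0.025^(1/n).

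| k | Result | Sensitivity | Lower limit | Turns lost, % of 150 |
|---|---|---|---|---|
| 0 | 150/150 | 100% | 97.6% | 0 (0%) |
| 1 | 145/145 | 100% | 97.5% | 5 (3.3%) |
| 2 | 140/140 | 100% | 97.4% | 10 (6.7%) |
| 3 | 135/135 | 100% | 97.3% | 15 (10.0%) |

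The estimate does not move and the limit moves by 0.3 points.

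**4. Lighter loss.** If each withdrawn subject misses only the fifth turn, k = 1, 2, 3 loses 1, 2 or 3 turns, or 0.7%, 1.3% and 2.0% of 150.

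**5. Imperfect detection.** With about 95% of performed turns detected, rounded to whole turns, k = 0 gives 142/150 = 94.7% (exact 95% interval 89.8% to 97.7%). k = 3 with five turns lost each gives 128/135 = 94.8% (89.6% to 97.9%). The two results are practically the same.

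**6. Failure while turns are being performed.** Read literally, 9.3.1 and 9.3.3 count such turns as missed. If one, two or three subjects had all five turns missed in this way and all other turns were detected, the result would be 145/150 = 96.7%, 140/150 = 93.3% or 135/150 = 90.0%. A failure of this kind therefore lowers the figure. Only turns that never took place are left out.

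**7. Which device.** Sections 1 and 2.1 attach the word device to INVSENSOR00011. Section 9.1 speaks of the device's output when it means that sensor, and 9.3.5 speaks of the device's specificity in the same sense. No readable text uses the bare singular for a control device.

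**8. Would a shortfall show?** The totals 145, 140 and 135 in step 3 lie visibly below the stated floor of 150. This check has a limit: five is a minimum. If every subject performed six turns (an assumption), three full withdrawals would leave 27 × 6 = 162, which is above 150.

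**9. Could lost turns be counted?** A count of turns not assessed needs a fixed number per subject. The readable text gives only a minimum. The schedule may lie in the redacted parts of section 7.5.

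**The case for a change.** The strongest case for a change is that it would be cheap and the figure may travel. Section 9.1 calls the data validation data and section 7.5.7 foresees regulatory use. An outside reader would want to know whether 100% was reached with the sensor working in all 30 subjects or in 27. One term defined in section 5.3 and a reporting line in 9.3 would settle this without touching the formula, the sample size or the procedures. As worded, two operators could also treat a fault in a reference device differently.

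Part of this stands. Section 5.3 does leave the device unnamed, and readable 9.3 does not bring malfunction withdrawals next to the sensitivity. But the events are not lost: section 10 has them recorded and reported, so the number withdrawn for malfunction should be recoverable. The formula also yields a numerator and a denominator, and a report that prints both shows the base on which the percentage rests. A mandatory count of turns not performed could not be met from the readable text, for the reason in step 9. Redactions in sections 7.5, 8, 10 and 11.3.2 may already cover sensor checks, replacement or reporting.

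**Conclusion.** No change to the plan is needed. Followed as written, it gives a sound sensitivity for the turns performed. The size of the matter, with up to three of 30 subjects lost before any scored turn and perfect detection otherwise, is no movement in the estimate and 0.3 points in the lower limit. With no malfunction it is zero. No decision depends on it, because section 8 sets no criterion to pass.

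This rests on assumed counts of withdrawals, on independent turns as section 9.1 states, on five turns per subject, and on the literal reading that performed but undetected turns are missed detections. What remains is a gap that analysts fill as a matter of course, by giving numerator and denominator with the percentage and stating how many subjects were withdrawn for malfunction, by device. The unnamed device in section 5.3 is a loose term with a natural reading. The sponsor may clarify it at any time, and the analysis does not depend on it.

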6. EQUIPMENT AND MATERIALS

Equipment and Materials: All lab equipment will be maintained per manufacturer specifications and all study personnel will be trained on the use of relevant equipment.

Test Devices:

- INVSENSOR00011
- Root [REDACTED]

Control Devices:

- Masimo Radical-7
- Masimo pulse oximeter sensor
- Masimo RAM sensor

Research Equipment:

- Data Collection Laptop, software and other equipment as necessary to record the data

7. PROCEDURES

7.1. **Advertisement and Recruitment**

7.1.1. Our Web Ad [REDACTED] will be posted publically on craigslist or similar websites.

7.2. **Phone Screening**

- 7.2.1. Once the potential subject sees the recruitment material (i.e. Web Ad), they contact our clinical schedulers to elicit more details about the screening. The phone screening is handled by designated clinical staff that is trained for screening/scheduling.
- 7.2.2. Appointments are made once the phone screening process is completed and the person screening the subject determines they qualify for screening based on the Recruitment Script [REDACTED]
- 7.2.3. If the person does not qualify at this time their information will not be kept.

7.3. Consent Process.

- 7.3.1. Have each volunteer read and sign the correct forms which include the consent form [REDACTED] Gender and Ethnicity Questionnaire [REDACTED] and Confidentiality Agreement [REDACTED]. The consent form must be stamped with current IRB approval. No study related activities will be conducted until consent is signed.
- 7.3.2. Subject demographic information including age, gender, height, weight, and ethnicity may be collected. In addition, a brief medical history and vital signs may be recorded.

7.4. Screening:

- 7.4.1. Have each subject complete [REDACTED] – Health Assessment Questionnaire.
- 7.4.2. Female volunteers of child bearing potential will be required to take a pregnancy test as part of screening. A positive pregnancy test will disqualify them from the study.
- 7.4.3. If the subject does not pass screening, he/she will be compensated [REDACTED] for travel.

7.5. Study Procedure

- 7.5.1. Apply sensors. [REDACTED]

- 7.5.2. [REDACTED]

- 7.5.3. [REDACTED]

[REDACTED]	[REDACTED]	[REDACTED]

[REDACTED]	[REDACTED]	[REDACTED]
[REDACTED]	[REDACTED]	[REDACTED]
[REDACTED]	[REDACTED]	[REDACTED]

7.5.4. [REDACTED] All enrolled subjects will be paid [REDACTED] after the completion of the study with no additional compensation for travel. Subjects who do not complete the study will be paid [REDACTED] with no additional compensation for travel.

7.5.5. In case of an error in following the instruction set, subject can repeat the missed steps.

7.5.6. Subjects may stop the study at any time.

7.5.7. Data collected in this study may be used in the future for product development, publications, and/or submissions to the FDA or other regulatory agencies.

7.6. Discontinuation

[figure not shown]
7.6.1. In the event that a study is discontinued prior to completion, whether it is due to the investigator's discretion or the subject's request, the subject will be paid for their time according to the Financial Compensation chart, refer to Section 7.5.4.

7.7. Protocol Deviation

7.7.1. If there is a protocol deviation it shall be recorded on the Case Report Form. The Protocol Deviation Report [REDACTED] shall also be completed.

8. ACCEPTANCE CRITERIA (IF APPLICABLE)

There are no acceptance criteria. [REDACTED]

9. SAMPLE SIZE JUSTIFICATION AND DATA ANALYSIS PROCEDURE TO BE USED

9.1. Sample Size Determination

In each subject, the protocol induces at least five position changes during the study. To assess INVSENSOR00011's detection capability, the device output will be compared against observer's notes for each change. Assuming a sample size $N = 30$, there will be at least 150 independent data points collected, which will be used for validation. This data will be enough for calculating sensitivity and specificity of the position detection algorithm.

9.2. For heart rate and respiration rate comparison, the study does not have an accuracy requirement to meet. However, INVSENSOR00011's heart rate and respiration rate measurements will be compared against reference measurements for an assessment. $N=30$ is deemed sufficient for a qualitative assessment of performance.

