9.4. Expected Dropout Rates

Subjects may not complete the study for various reasons, such as a clinical screening test failure, at the Principal Investigator's discretion, or because the subject does not want to continue the study. Expected dropout rate for this study is approximately 0% of the total number of subjects enrolled.

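### Section 9.1 counts at least five position changes in each of 30 subjects as 150 independent data points, but they are repeated measures clustered by subject

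*Combined protocol and SAP*

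**What the plan says.** Section 9.1 starts from the subject: "In each subject, the protocol induces at least five position changes during the study". It states the unit of comparison: "the device output will be compared against observer's notes for each change". With 30 subjects it then reaches the total: "there will be at least 150 independent data points collected, which will be used for validation". The sufficiency claim rests on that total: "This data will be enough for calculating sensitivity and specificity of the position detection algorithm".

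Section 9.3 compares the device with the notes at each turn. In 9.3.4 it forms sensitivity as detected changes over detected plus missed changes, pooled over subjects. The visible text of 9.3 has no subject-level summary, no confidence interval and no other allowance for repeated turns in one person. Section 8 opens with "There are no acceptance criteria"; the text after that is redacted. Most of the procedure in 7.5.1 to 7.5.3 is also redacted, so the actual number of turns per subject cannot be seen. Section 7.5.5 lets a subject repeat missed steps.

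**The concern.** The section contradicts itself within a few lines: it says the changes are induced several at a time in each subject, then treats every change as a separate independent observation. A subject's turns share one body, one sensor application (on the chest or the back, per Section 1) and one session. If the device misses one turn in a subject because of fit or body shape, it may well miss another. The documents neither argue that this correlation is zero nor allow for it.

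The count of 150 is the only quantitative support for the claim that the data suffice. Section 7.5.7 says the data may go into publications or regulatory submissions. A reader told that there are 150 independent points would naturally attach binomial precision on 150 to the reported sensitivity.

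**Working it through.** **Inputs from the documents.** N = 30 subjects and m = at least 5 changes per subject (9.1). Dropout is taken as nil, since 9.4 states: "Expected dropout rate for this study is approximately 0% of the total number of subjects enrolled". The documents give no ICC, no expected sensitivity, no confidence level and no precision target, so the values used below for the first three are assumptions.

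**Step 1: reproduce the plan's figure.** N x m = 30 x 5 = 150. The figure is correct as a minimum count of position changes.

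**Step 2: information in those changes.** With equal numbers of changes per subject, the design effect is DE = 1 + (m - 1) x ICC and the effective number of independent observations is N x m / DE. At exactly m = 5:

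| Assumed ICC | DE | Effective n |
|---|---|---|
| 0 | 1.0 | 150 |
| 0.1 | 1.4 | 150/1.4 = 107 |
| 0.3 | 2.2 | 150/2.2 = 68 |
| 0.5 | 3.0 | 150/3.0 = 50 |

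**Step 3: more than five changes.** The plan says at least five. As m grows, N x m / DE rises towards N / ICC, which is 30/0.1 = 300, 30/0.3 = 100 and 30/0.5 = 60. At ICC 0.1, nine changes per subject give 270/1.8 = 150. So 150 independent-equivalent observations can be reached with enough turns if the ICC is below 0.2 (30/0.2 = 150). They cannot be reached at 0.3 or 0.5 however many turns are made.

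**Step 4: what this does to precision.** Take a hypothetical result of 8 misses in 150 changes, five per subject, so p = 142/150 = 94.7%. An exact 95% interval on 150 is 89.8% to 97.7% however the misses fall. For comparison, use one interval that accounts for subject: variance = (30/29) x sum of (x_i - 5p)^2 / 150^2, where x_i is the number detected in subject i; carry this to the logit scale by the delta method, with t(0.975, 29 df) = 2.045.

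- Four subjects miss two each: the sum of squares is 13.87, SE = 0.0252, logit SE = 0.0252/(0.947 x 0.053) = 0.50. The interval is 86.5% to 98.0% (estimated ICC 0.22).
- Three subjects miss 3, 3 and 2: the interval is 83.9% to 98.4% (estimated ICC 0.42).
- Eight subjects miss one each: the interval is 90.1% to 97.2% (estimated ICC -0.05).

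The widths are 11.5, 14.5 and 7.1 points, against 7.9 for the exact interval on 150. The same eight misses support quite different precision depending on how they are spread over subjects. In the third pattern the independence assumption does no harm.

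**The case against.** The strongest reply is that nothing visible in the plan uses 150 as independent. Section 9.1 claims only that the data are enough to calculate sensitivity and specificity. Section 9.3 plans counts and a ratio, and Section 8 says there are no acceptance criteria. This stands, and it keeps the point minor. It does not make the statement in 9.1 true, and 9.1 is where a reader learns how much information the sample holds.

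Three stronger readings are tempting, and the documents do not support them.

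- *The sensitivity estimate is wrong.* A reader might infer this from the missing subject term. With equal turns per subject, clustering does not bias the pooled proportion; it affects its precision. Repeats under 7.5.5 could make the turns unequal, but the visible text does not show that they will.
- *The study will report an interval that is too narrow.* In a beta-binomial simulation of 30 subjects with five changes each, at an assumed sensitivity of 95%, a nominal 95% exact interval on 150 covers about 92%, 84% and 76% at ICC 0.1, 0.3 and 0.5. The visible plan proposes no such interval, so these losses would arise only if someone later computed one.
- *The sample is worth 150 only if the correlation is zero.* That holds at exactly five changes per subject. Step 3 shows that more turns can offset a small positive correlation, and the number of turns is redacted.

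It is also fair to say that the ICC may be close to zero. The documents do not settle this either way, which is why independence should not be asserted.

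**Conclusion.** The point holds and is minor. Calling the position changes independent claims a property that the design does not provide and that the visible plan does not justify. The supported description is at least 150 changes clustered in 30 subjects. The overstatement could be nil at zero correlation. At exactly five changes per subject it would take the effective number down to about 107, 68 or 50 at ICC 0.1, 0.3 or 0.5. These sizes rest on an assumed ICC and on equal numbers of turns. No stated power, test or pass/fail decision changes. What is affected is the sample-size justification and how precisely the reported sensitivity would be read.

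**What to change.** In 9.1, replace the phrase about independent data points with: 'at least 150 position changes clustered in 30 subjects'. Then add: 'With exactly five changes per subject, the effective number of independent observations would be about 107, 68 and 50 at assumed within-subject correlations of 0.1, 0.3 and 0.5.' The condition of exactly five is needed, because the figures are higher with more turns.

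In 9.3.4, keep the formula and add: 'Sensitivity will be reported with a 95% CI that accounts for clustering by subject, together with the number of subjects with any missed change.' The choice of method is the sponsor's. It should cover the case of no missed change, where the logit interval used above is undefined.

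The cost is one phrase and one sentence in 9.1 and one sentence in 9.3.4, with no extra subjects. The stated precision becomes less favourable and the interval will usually be wider, though not always, as the third pattern in the example shows.
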